3.3 EXPLORATORY OBJECTIVES & HYPOTHESES

Objective 1: To determine the effect of pembrolizumab on restoring donor chimerism in patients with relapsed myeloid malignancies and mature B cell lymphomas following alloSCT.

Objective 2: To determine the effect of pembrolizumab on the numbers and activations status of peripheral blood T cells.

Objective 3: To compare PD-L1 expression on malignant cells at initial diagnosis and at disease relapse following alloSCT.

Objective 4: To examine the effect of pembrolizumab on the T cell receptor (TCR) repertoire in the peripheral blood, and where available, tumor environment, following alloSCT.

Hypothesis 1: Pembrolizumab treatment will restore donor chimerism when administered to patients with relapsed myeloid malignancies and mature B cell lymphomas following alloSCT.

Hypothesis 2: Pembrolizumab treatment will be associated with enhanced expression of activation markers on peripheral blood T cells in patients with relapsed myeloid malignancies and mature B cell lymphomas following alloSCT.

Hypothesis 3: PD-L1 expression will be increased on malignant cells following disease relapse after alloSCT compared to diagnosis.

Hypothesis 4: Pembrolizumab treatment will be associated with clonal expansion of conventional and regulatory T cell subsets in peripheral blood as measured by TCR- β deep sequencing and Simpson's index of diversity analysis.

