Effect of pembrolizumab on T cell number and activation status. Pembrolizumab, by interrupting PD-1/PD-L1 interactions, may affect not only numbers of T cells present in peripheral blood (and bone marrow), but may also lead to upregulation of activation markers on peripheral blood T cells. To explore this hypothesis, the frequencies and absolute numbers of T cell subsets (conventional CD4+ and CD8+ and CD4+CD25+CD127- regulatory T cells (Tregs)) will be enumerated in the peripheral blood (all patients) and bone marrow (AML and MDS patients only) at several defined time points prior to and following pembrolizumab treatment (pre-treatment, and at 3, 6, 9, 12, 15, 18, and 24 months of treatment). Peripheral blood mononuclear cells (PBMC) or bone marrow cells will be stained with anti-CD3, anti-CD8, anti-CD4, anti-CD25, and

anti-CD127 antibodies and analyzed by flow cytometry to define specific T cell subsets. Conventional CD4+ T cells will be defined as CD3+CD4+CD25-/low cells, while conventional CD8+ T cells will be defined as CD3+CD8+ cells. Tregs will be defined as CD3+CD4+CD25hiCD127- cells. Frequencies will be calculated by sub-gating on the lymphocyte population as appropriate. Absolute numbers of T cells in each subset will be enumerated by multiplying the frequency of each T cell subset by the total white blood count from each sample. T cell activation status will be analyzed by co-staining cells with antibodies directed against the following markers: HLA-DR, CD69, ICOS and CD25 (others may be added). Descriptive statistics will be utilized to compare pre- and post-treatment frequencies, absolute numbers and activation status of T cells in enrolled patients. The goal would be to define potential biomarkers associated with responsiveness to pembrolizumab treatment that could be verified in larger studies in a similar patient population.

Detection of PD-L1 and PD-L2 expression. To determine whether expression of PD-1 ligands on malignant or non-malignant cells in the tumor environment may be a driver of disease relapse following alloSCT, PD-L1 and PD-L2 expression will be analyzed and compared between diagnostic samples and post-alloSCT relapse samples. This assay will be performed in collaboration with Merck using in-house protocols.

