TCR sequencing. To investigate the hypothesis that pembrolizumab treatment will be associated with clonal expansion of antigen-specific T cells, the peripheral blood TCR repertoires will be compared in each patient prior to and at defined time points following pembrolizumab treatment (see above) using TCR- β deep sequencing. These studies will be performed by Adaptive Biotechnologies, and data analyzed internally. Simpson's index of diversity will be utilized to compare the diversity of TCR repertoires prior to and following pembrolizumab treatment

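### Simpson's index, the only summary statistic named for T-cell clonal expansion, can miss or mis-sign expansion of clones that start rare; a clone-level comparison should be added

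*Combined protocol and SAP*

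**What the plan says.** Exploratory Hypothesis 4 in Section 3.3 predicts: "Pembrolizumab treatment will be associated with clonal expansion of conventional and regulatory T cell subsets in peripheral blood". It is to be measured by TCR-beta "deep sequencing and Simpson's index of diversity analysis".

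The TCR sequencing paragraph of Section 5.5 sets out to investigate whether "pembrolizumab treatment will be associated with clonal expansion of antigen-specific T cells". It plans a within-patient comparison: "the peripheral blood TCR repertoires will be compared in each patient prior to and at defined time points following pembrolizumab treatment". It then names one statistic: "Simpson's index of diversity will be utilized to compare the diversity of TCR repertoires prior to and following pembrolizumab treatment".

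No formula for the index is given (for example 1 - S or 1/S), and no expected direction, threshold or clone-level statistic. Section 9 does not mention the TCR data. The other T-cell readouts in Section 5.5 are flow-cytometry measures: "Descriptive statistics will be utilized to compare pre- and post-treatment frequencies, absolute numbers and activation status of T cells in enrolled patients". They count and phenotype T cells but do not measure clonality.

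**The concern.** The hypothesis is about individual clones growing, while the named statistic is one number for the whole repertoire. Clone frequencies sum to 1, so growth in some clones shrinks the share of all the others. Squaring gives most of the weight to the largest clones. If rare clones grow while a few large clones are diluted, the loss from the large clones can exceed the gain from the growing ones, and the repertoire then reads as more diverse.

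At stake is the answer to exploratory Objective 4. In a study of 12 to 26 patients, a null or inverted summary could discard a lead. For the neighbouring T-cell assays, Section 5.5 says that leads are meant to be verified in larger studies.

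**Working it through.** The documents give no figure for the TCR readout, so there is nothing to reproduce. Baseline S, the number of expanding clones, their fold-change and the sequencing depth are all absent from the documents and are assumed below.

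**One expanding clone.** Let a clone go from frequency f0 to f while all others are diluted proportionally. Let R be the sum of squares among the other clones, renormalised to 1.

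S(f) = f² + (1 - f)²R

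S(f) - S(f0) = (f - f0)[(f + f0)(1 + R) - 2R]

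For an expansion (f > f0), S falls exactly when f < 2R/(1+R) - f0. This is possible only if f0 < R/(1+R). For a clone starting near zero the limit is close to 2S: 2.00 times S at R = 0.001, 1.98 at 0.01 and 1.90 at 0.05.

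With R = 0.01:
- 0.01% to 1.5% (150-fold): S goes from 0.009998 to 0.009927 (-0.7%), the wrong direction.
- 0.01% to 2.05%: S goes to 0.010014 (+0.2%), the right direction.
- 1.0% to 1.8%: S goes from 0.009901 to 0.009967 (+0.7%), the right direction although the clone ends below 2S.

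The largest relative fall that one clone can cause is R/(1+R): 1.0% at R = 0.01 and 4.8% at R = 0.05. For k clones it is kR/(1+kR). Ten clones give 0.1/1.1 = 9% at R = 0.01 and 0.5/1.5 = 33% at R = 0.05.

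**Several expanding clones.** S_post = (S - k·f0²)·[(1 - k·f1)/(1 - k·f0)]² + k·f1²

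For k = 20, f0 = 0.01%, f1 = 0.2%, the bracket is (0.96/0.998)² = 0.9253 and the added term is 20 × 0.002² = 0.00008. At S = 0.012, S_post = 0.0119998 × 0.9253 + 0.00008 = 0.01118, a change of -6.8%.

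| Baseline S | 20 clones, 0.01% to 0.2% | 10 clones, 0.01% to 0.5% |
|---|---|---|
| 0.0005 | +8.5% | +40% |
| 0.002 | -3.5% | +2.9% |
| 0.005 | -5.9% | -4.6% |
| 0.012 | -6.8% | -7.5% |
| 0.05 | -7.3% | -9.1% |

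The sign changes at S of about 0.0011 in the first case and 0.0026 in the second. For scale, a single 10% clone contributes 0.1² = 0.010 to S on its own.

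**Sampling noise.** Under multinomial sampling alone, the SD of the relative pre/post change in S was about 5% at 20,000 templates and 2.2% at 100,000 for S near 0.011. For S near 0.0015 it was about 6% and 2.7%. Taking 6% and 2.5% as round figures, the -3.5% shift is 0.6 and 1.4 SD, and the -6.8% shift is 1.1 and 2.7 SD.

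In 400 simulated pairs of the 20-clone case, the observed S moved the wrong way in these proportions (50% would be expected with no change):

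| Baseline | 20,000 templates | 100,000 templates |
|---|---|---|
| S about 0.0034 | 78% | 96% |
| One 10% clone, S about 0.010 | 88% | 99.5% |
| S about 0.05 | 99% | 100% |

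**What the same data can show clone by clone.** A Fisher test per clone at 0.05/5000 detects a rise from 0.01% to 0.2% with power of about 0.99 at 20,000 templates and 1.00 at 50,000 and 100,000. This counts sampling error only.

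**The case against.** Four objections have force.

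*Scope.* A reader might infer that any clone ending below 2S makes the repertoire look more diverse. That is false. At S = 0.012, a clone going from 1.0% to 2.0% ends at 1.67 times S, yet S rises by 0.5%. The reversal needs clones that start rare.

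*Only planned readout.* A reader might also infer that the plan rules out any other analysis. It does not. Both sections name deep sequencing alongside the index, and Section 5.5 plans a comparison within each patient. A clone-level comparison is left unspecified, not excluded.

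*Size.* The percentages are for S. The plan does not say which form of the index it means. In the 1 - S form, the S = 0.012 example moves only from 0.9880 to 0.9888; a change near 7% appears only in the 1/S form. At low depth or low S the shift is often within sampling noise, so the usual result there is no clear change. All decisive inputs are assumed, no passage describes these patients' repertoires as oligoclonal, and at low S the index moves the right way.

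*The remedy.* Fisher's test ignores biological drift and overdispersion between blood draws. A single-arm trial cannot attribute an expanded clone to treatment.

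All four narrow the point. None supplies a clone-level statistic where the hypothesis needs one, and noise does not remove a reversal when many rare clones expand at good depth.

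**Conclusion.** The point holds as a minor one. Simpson's index is the only named summary statistic for a hypothesis about clonal expansion, and it can give a null or wrong-signed answer when the expanding clones start rare and finish below about 2S. In the assumed 20-clone example the shift in S runs from +8.5% to -7.3% across baseline S of 0.0005 to 0.05, and turns negative above about 0.0011.

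A reader might infer that the trial will report real expansion as its opposite. The documents do not support that. They give no baseline S, clone sizes or depth. With one rare clone expanding, the wrong-signed shift is at most R/(1+R) and often within noise, so a missed expansion is the likelier outcome. A visible reversal needs many rare clones expanding or an oligoclonal baseline, with adequate depth. The DLT endpoint, ORR, DOR, OS and the sample size are unaffected.

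**What to change.** In Section 5.5 and Hypothesis 4:

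- Add a prespecified paired comparison, in each patient, of every clone's template count before and after treatment. Control the false-discovery rate, and require a minimum fold-change or allow for overdispersion. The documents describe no replicate samples from which to estimate overdispersion, so a minimum fold-change may be the more practical choice.
- Report the number of expanded clones and the share of the repertoire they occupy.
- Keep Simpson's index as a secondary descriptor of overall diversity, with its formula and expected direction stated.
- Describe expanded clones as changed on treatment, not as caused by it, because there is one arm and no control.

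The cost is a little more analysis work on sequencing data already planned. No new samples or assays are needed.

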6.0 METHODOLOGY

6.1 ENTRY CRITERIA

6.1.1 DIAGNOSIS FOR STUDY ENTRY

Male or female subjects with AML, MDS or mature B cell lymphomas that have relapsed following matched-related donor (MRD) or matched unrelated donor (MUD) (HLA-A -B -C -DR -DQ) alloSCT are eligible for enrollment.

6.1.2 SUBJECT INCLUSION CRITERIA

1. Signed written informed consent

- a) Subjects must have signed and dated an IRB-approved written informed consent form in accordance with regulatory and institutional guidelines. This must be obtained before the performance of any protocol-related procedures that are not part of normal subject care.

- b) Subjects must be willing and able to comply with scheduled visits, treatment schedule, laboratory tests and other requirements of the study.

2. Target population

- a) Subjects must be ≥ 18 years of age.
- b) Subjects must have an ECOG performance status of 0-1 (Appendix).
- c) Subjects have undergone alloSCT > 90 days prior to enrollment from a matched-related donor (MRD), matched-unrelated donor (MUD), cord blood donor, or haplo-identical and cord blood donor.
- d) There must be histological confirmation of relapse after alloSCT of any of the following diseases: any mature B cell lymphoma (cHL or NHL), AML or MDS.
- e) Subjects must be off of all immunosuppressive medications for a minimum of 2 weeks with the exception of physiologic doses of corticosteroids.
- f) Subjects with B cell lymphoma must have measurable disease, defined as at least 1 lesion that can be accurately measured in at least 2 dimensions with CT scan. Minimum measurement must be > 15 mm in the longest diameter and > 10 mm in the short axis.
- g) Subjects must not have had any prior investigational agents or devices within 4 weeks of beginning study drug
- h) Subjects must have no prior history of VOD
- i) Subjects must demonstrate adequate organ function as defined in **Table 2**. All screening labs should be performed within 10 days of treatment initiation.

Table 2. Adequate Organ Function Laboratory Values

System	Laboratory Value
Hematological	
Absolute neutrophil count (ANC)	≥ 500 /mCL
Platelets	$\geq 20,000$ /mCL
Hemoglobin	≥ 8 g/dL (RBC transfusions are OK)
Renal	
Serum creatinine OR Measured or calculated ^a creatinine clearance (GFR can also be used in place of creatinine or	≤ 1.5 X upper limit of normal (ULN) or ≥ 60 mL/min for subject with creatinine levels > 1.5 X institutional ULN

CrCl)	
Hepatic	
Serum total bilirubin	$\leq 1.5 \times \text{ULN}$ or direct bilirubin $\leq \text{ULN}$ for subjects with total bilirubin levels $> 1.5 \times \text{ULN}$
AST (SGOT) and ALT (SGPT)	$\leq 2.5 \times \text{ULN}$
Albumin	$\geq 2.0 \text{ mg/dL}$
Coagulation	
International Normalized Ratio (INR) or Prothrombin Time (PT)	$\leq 1.5 \times \text{ULN}$ unless subject is receiving anticoagulant therapy, in which case, the PT/INR should be within therapeutic range for intended use.
Activated Partial Thromboplastin Time (aPTT)	$\leq 1.5 \times \text{ULN}$ unless subject is receiving anticoagulant therapy, in which case, the PTT should be within therapeutic range for intended use.
^a Creatinine clearance should be calculated per institutional standard.	

- j) Female subjects of childbearing potential should have a negative urine or serum pregnancy test (β -hCG) within 72 hours prior to receiving the first dose of study medication.
- k) Female subjects with childbearing potential should be willing to use 2 methods of contraception, be surgically sterile, or abstain from heterosexual activity throughout the course of the study, until 120 days after the final dose of study medication. Subjects with childbearing potential are those who have not been surgically sterilized or have not been free from menses for > 1 year. Abstinence is acceptable if this is the established and preferred contraceptive method for the subject (see Section 6.7.1).
- l) Male subjects should agree to use an adequate method of contraception starting with the first dose of study medication until 120 days after the final dose of study medicine. Abstinence is acceptable if this is the established and preferred contraceptive method for the subject (see Section 6.7.1).

6.1.3 SUBJECT EXCLUSION CRITERIA

1. Target disease exclusions

- a) Subjects must not have known central nervous system involvement by disease (parenchymal, meningeal or cerebrospinal fluid)

2. Medical history, concurrent diseases, and prior treatments

- a) Subjects must not have a history of any positive test for hepatitis B or hepatitis

C indicating active disease or previous exposure.

- b) Subjects must not have a history of human immunodeficiency virus (HIV) infection.
- c) Subjects must not be receiving systemic steroid therapy or any other form of immunosuppressive therapy within 2 weeks prior to the first dose of study medication. The use of physiologic doses of corticosteroids is acceptable.
- d) Subjects must not be concurrently receiving disease-modifying therapy in another therapeutic investigational study.
- e) Subjects must not have received a prior monoclonal antibody within 4 weeks prior to the first dose of study medication, and must have recovered (\leq grade 1) from adverse events related to any anti-cancer agent administered $>$ 4 weeks previous to the first dose of study medication.
- f) Subjects must not have received chemotherapy or targeted small molecule therapy within 4 half-lives of the specific agent(s), or radiation therapy within 2 weeks prior to the first dose of study medication, and must have recovered (\leq grade 1) from adverse events related to a previously administered agent.
- g) Subjects must not have received a donor lymphocyte infusion (DLI) within 8 weeks prior to the first dose of study medication.
- h) Subjects must not have a history of severe (grade 3-4) acute GVHD, and/or current $>$ grade 1 acute GVHD. Subjects must not have a history of active chronic GVHD (whether limited or extensive stage).
- i) Subjects must not have autoimmune disease that has required systemic treatment in the past 2 years (i.e. with use of disease modifying agents, corticosteroids or immunosuppressive drugs). Replacement therapy (e.g., thyroxine, insulin, or physiologic corticosteroid replacement therapy for adrenal or pituitary insufficiency, etc.) is not considered a form of systemic treatment.
- j) Subjects must not have a known history of congestive heart failure, unstable angina pectoris, or cardiac arrhythmia (with the exception of chronic and rate-controlled atrial fibrillation).
- k) Subjects must not have a history of other serious underlying medical or psychiatric condition that, in the opinion of the investigator, would impair the ability to receive, tolerate and or comply with the planned treatment and follow-up.
- l) Subjects must not have a history of a known secondary primary malignancy that is not in remission and/or that requires active therapy. Exceptions include non-melanoma skin cancers and in situ cervical cancer that has undergone

curative-intent local therapy.

- m) Subjects must not have a known active infection requiring intravenous antibiotic therapy.
- n) Subjects must not have a history of (non-infectious) pneumonitis that required steroid treatment, evidence of interstitial lung disease, or active, non-infectious pneumonitis. Subjects must not have active, non-infectious colitis.
- o) Subjects must not be pregnant or breastfeeding, or expecting to conceive or father children within the projected duration of the trial, starting with the screening visit through 120 days after the final dose of study medication.
- p) Subjects must not have received a live vaccine within 30 days prior to the first dose of study medication.
- q) Subjects must not be or have an immediate family member (spouse, parent, legal guardian, sibling or child) who is an investigational site sponsor or staff directly involved with the trial, unless IRB approval is granted previously.

6.2 TRIAL TREATMENTS

The treatment to be used in this trial is outlined below in **Table 3**.

Table 3. Trial treatments

Study Drug	Dose	Cycle duration	Route of administration	Treatment period	Use
Pembrolizumab	200 mg in 100 mL of normal saline	21 days	IV infusion (0.2 micron in-line filter) over 30 minutes	Day 1 of each treatment cycle	Experimental

The investigator shall take responsibility for and shall take all steps to maintain appropriate records and ensure appropriate supply, storage, handling, distribution and usage of the study medication in accordance with the study protocol and any applicable laws and regulations.

6.2.1 DOSE SELECTION/MODIFICATION

6.2.1.1 DOSE SELECTION (PREPARATION)

All subjects will receive 200 mg of pembrolizumab via IV infusion every 21 days. Details on preparation and administration are provided in the pharmacy manual.

The rationale for selection of pembrolizumab dose to be used in this trial is provided in Section 5.2. There are no specific clarifications or evaluations required to be performed in order to administer the proper dose to each subject.

6.2.1.2 DOSE MODIFICATION

Pembrolizumab will be withheld for drug-related, grade 4 hematologic toxicities and drug-related \geq grade 2 or 3 toxicities including laboratory abnormalities, as outlined in **Tables 4 and 5**. Attribution of events to drug will be per investigator/physician discretion.

Table 4. Dose modification guidelines for hematological drug-related adverse events

Toxicity	Grade	Hold Treatment (Y/N)	Timing for restarting treatment	Discontinue Subject (after consultation with the Principal Investigator)
Hematological Toxicity	1, 2, 3	No	N/A	N/A
	4	Yes	Toxicity resolves to Grade 0-1 or baseline	Toxicity does not resolve within 12 weeks of last infusion Permanent discontinuation should be considered for any life-threatening event

Table 5. Dose modification guidelines for non-hematological drug-related adverse events

Toxicity	Hold Treatment For Grade	Timing for Restarting Treatment	Discontinue Subject
Acute GVHD (as defined by the Gluckenberg scale - see appendix)	2 ¹	Toxicity resolves to grade 0-1. Re-start pembrolizumab at 200 mg IV q21 days.	Toxicity does not resolved within 12 weeks of last dose or inability to reduce corticosteroid to 10 mg or less of prednisone equivalent per day within 12 weeks.
	3-4 ¹	Permanently discontinue	Permanently discontinue

Toxicity	Hold Treatment For Grade	Timing for Restarting Treatment	Discontinue Subject
Diarrhea/Colitis	2 ¹	Toxicity resolves to Grade 0-1. Re-start pembrolizumab at 200 mg IV q21 days.	Toxicity does not resolve within 12 weeks of last dose or inability to reduce corticosteroid to 10 mg or less of prednisone or equivalent per day within 12 weeks.
	3-4 ¹	Permanently discontinue	Permanently discontinue
Hypophysitis	2-3 ¹	Toxicity resolves to Grade 0-1.	Toxicity does not resolve within 12 weeks of last dose or inability to reduce corticosteroid to 10 mg or less of prednisone or equivalent per day within 12 weeks.
	4 ¹	Toxicity resolves to Grade 0-1	Toxicity does not resolve within 12 weeks of last dose or inability to reduce corticosteroid to 10 mg or less of prednisone or equivalent per day within 12 weeks.
AST, ALT, or Increased Bilirubin	2 ¹	Toxicity resolves to Grade 0-1. Re-start pembrolizumab at 200 mg IV q21 days.	Toxicity does not resolve within 12 weeks of last dose.
	3-4 ¹	Permanently discontinue (see exception below) ²	Permanently discontinue
Hyperthyroidism or Hypothyroidism	3 ¹	Toxicity resolves to Grade 0-1	Toxicity does not resolve within 12 weeks of last dose or inability to reduce corticosteroid to 10 mg or less of prednisone or equivalent per day within 12 weeks.
	4 ¹	Permanently	Permanently discontinue

Toxicity	Hold Treatment For Grade	Timing for Restarting Treatment	Discontinue Subject
		discontinue	
Infusion Reaction	3-4	Permanently discontinue	Permanently discontinue
Neurologic events (including myasthenia gravis)	2 ¹	Toxicity resolves to Grade 0-1. Re-start pembrolizumab at 200 mg IV q21 days.	Toxicity does not resolve within 12 weeks of last dose or inability to reduce corticosteroid to 10 mg or less of prednisone or equivalent per day within 12 weeks.
	3-4 ¹	Permanently discontinue	Permanently discontinue
Pneumonitis	2 ¹	Toxicity resolves to Grade 0-1. Re-start pembrolizumab at 200 mg IV q21 days.	Toxicity does not resolve within 12 weeks of last dose or inability to reduce corticosteroid to 10 mg or less of prednisone or equivalent per day within 12 weeks.
	3-4 ¹	Permanently discontinue	Permanently discontinue
Renal Failure or Nephritis	2 ¹	Toxicity resolves to Grade 0-1. Re-start pembrolizumab at 200 mg IV q21 days.	Toxicity does not resolve within 12 weeks of last dose or inability to reduce corticosteroid to 10 mg or less of prednisone or equivalent per day within 12 weeks.
	3-4 ¹	Permanently discontinue	Permanently discontinue
All Other Drug-Related Toxicity ³	3 Severe ¹ or	Toxicity resolves to Grade 0-1. Re-start pembrolizumab at 200 mg IV q21 days.	Toxicity does not resolve within 12 weeks of last dose or inability to reduce corticosteroid to 10 mg or less of prednisone or equivalent per day within 12 weeks.

Toxicity	Hold Treatment For Grade	Timing for Restarting Treatment	Discontinue Subject
	4	Permanently discontinue	Permanently discontinue

Note: Permanently discontinue for any severe or Grade 3 drug-related AE that recurs or any life-threatening event.
 
¹ Administer corticosteroid (See also Events of Clinical Interest Guidance Document and Section 8.2.3.2 Events of Clinical Interest).
 
² For patients with liver metastasis who begin treatment with Grade 2 AST or ALT, if AST or ALT increases by greater than or equal to 50% relative to baseline and lasts for at least 1 week then patients should be discontinued.
 
³ Patients with intolerable or persistent Grade 2 drug-related AE may hold study medication at physician discretion. Permanently discontinue study drug for persistent Grade 2 adverse reactions for which treatment with study drug has been held, that do not recover to Grade 0-1 within 12 weeks of the last dose.
 
* Attribution of events to drug will be per investigator/physician discretion; in case of DLT grade toxicity that is deemed to be unrelated to drug, patient can continue on trial with appropriate treatment
			

